### **15.0 Analytic Plan**

The data analysis follows a systematic process that begins with checking the data and ends with a rigorous test of specific hypotheses. Descriptive statistics and graphical procedures will be used to examine distributions of the outcomes and transformations of the data will be performed as needed.

#### ***15.1 Handling of Missing Data***

We routinely follow-up with research participants who do not return instruments during the specified time period, review returned instruments for missing items, and contact people to complete items, if multiple items were skipped to obtain all possible data. The first task is to assess whether the missing data are systematic. We plan to handle the issue of missingness in two steps. We will first compare the proportion of missing values between the two groups and if there is no significant difference, we will assume that the data has the "missing at random" (MAR) structure. We anticipate MAR structure for the repeated measures data. The PROC MIXED procedure in SAS that we will use is capable of producing optimal (maximum likelihood) estimators from the associated likelihoods.

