## **7.0 Research Design and Study Intervention**

Following baseline data collection, all participants will begin the 16-session core phase of the Group Lifestyle Balance (GLB) intervention. Percent weight change will be determined at the beginning of week 5, after 1 month of intervention. Those who achieve  $> 2.5\%$  weight loss will complete the remainder of the 12 GLB sessions. Those who achieve  $\leq 2.5\%$  weight loss will be stratified to the Group Lifestyle Balance Plus (GLB+) intervention (additional 12 sessions). A second round of data collection will

occur upon completion of the core intervention study phase, 4 months from baseline. Following this second data collection, participants will be matched into pairs based on gender and percent weight change at 4 months, and each person in a matched pair will be randomly assigned to treatment group for the extended intervention study phase. One person in each pair will receive either the standard GLB intervention or the augmented GLB+ intervention, and the second person in each pair will receive the alternate intervention. Following completion of the extended intervention study phase at 12 months, a third round of data collection will occur. A 6-month no contact phase will follow the extended intervention study phase to evaluate weight loss maintenance. The fourth and final round of data collection will occur upon completion of the 6-month no contact phase, 18 months from baseline.

The goals of both the GLB and GLB+ interventions include losing  $\geq 7\%$  of initial body weight and maintaining  $\geq 7\%$  weight loss through study end. The intervention group sessions will consist of 10-15 participants (to foster

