### **15.3 Specific Aim 2 Analysis**

It is hypothesized that participants randomized to GLB+ will on average maintain  $\geq 7\%$  weight loss at 12- and 18-months compared to participants randomized to GLB, who are expected to maintain an average loss of 5%. A multiple regression model using the matched pair design described above will be employed in two ways: first, using the percent change at 12- and 18-months as repeated measures nested within matched pairs, and second, as absolute changes using baseline, 12-, and 18-month weights. Significant covariates chosen will be incorporated into these models.

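### A non-significant difference in missing rates cannot support MAR; the Aim 2 models do not commit to 4-month weight change, and no not-at-random analysis of trial weights is planned

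*Combined protocol and SAP*

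**What the plan says.** Section 15.1 opens with a sound intention: "The first task is to assess whether the missing data are systematic. We plan to handle the issue of missingness in two steps". Only one step is labelled. It reads "We will first compare the proportion of missing values between the two groups and if there is no significant difference, we will assume" a missing-at-random structure. Nothing is said about what follows if the rates differ. The section then adds "We anticipate MAR structure for the repeated measures data" and names one method: "The PROC MIXED procedure in SAS that we will use is capable of producing optimal (maximum likelihood) estimators".

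Section 15.3 describes two Aim 2 models. The first works by "using the percent change at 12- and 18-months as repeated measures nested within matched pairs"; the second treats the data "second, as absolute changes using baseline, 12-, and 18-month weights". On covariates it says only "Significant covariates chosen will be incorporated into these models". The 4-month value is used at randomisation, where "participants will be matched into pairs based on gender and percent weight change at 4 months" (section 7.0; section 8.0 agrees). It is listed in neither model. The exploratory 18-month comparison of treatment sequences gives baseline weight as its example covariate.

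The only sensitivity analyses in the plan are in section 15.4.2, for the cost-effectiveness simulation.

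**The concern.** Comparing missing proportions between groups shows how many people are missing. It does not show whether being missing depends on the weight that was not seen, and that is the question MAR answers. A non-significant result is therefore presented as support that it cannot give.

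A likelihood-based mixed model is protected against drop-out only to the extent that the data in the model explain it. The 4-month percent change is known for everyone paired and is an obvious candidate to predict both drop-out and later weight. In the first Aim 2 model, a person who misses both the 12- and 18-month visits supplies no outcome. Whatever their 4-month weight says about them enters only through the pair partner, or if that variable happens to be selected.

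Two results are at stake. One is the GLB+ versus GLB contrast. The other is the pair of arm means: section 15.3 words its hypothesis as average losses of at least 7% and of 5%, and section 15.4.2 feeds each group's weight change into a model of progression to diabetes. The 18-month weight follows six months without contact, so some loss to follow-up is plausible. That people who regain attend less is an assumption.

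**Working it through.** The plan states no sample size, SD or drop-out rate, so it has no figure to reproduce. From the documents: expected losses of 7% (stated as a minimum) and 5%, taken as a true contrast of 2 points. Assumed: SD of percent change 5 or 7 points; 20% missing; drop-out odds ratio 2 or 3 per SD less loss; correlation of 4-month with follow-up change 0.6 or 0.8.

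**Step 1, the rule.** Two hypothetical cases are enough.
- Each arm loses 20 of 100. In GLB they are the 20 who regained most; in GLB+ they are a random 20. The rates are equal (20% and 20%), so the test passes, yet the data are not MAR.
- GLB loses a random 30% and GLB+ a random 10%. The rates differ, yet MAR holds because arm is in the model.

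In simulations with equal rates but weight-driven missingness in one arm (75 or 150 pairs, 10-30% missing), the rate test was significant in 3.5-6% of runs, about its nominal 5%.

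**Step 2, drop-out driven by 4-month weight in one arm only.** Pairs share the same 4-month value and follow-up is wholly missing. In GLB, logit P(missing) = a - ln(OR) x (4-month loss in SD units), with a set to give 20%; in GLB+ a random 20% are missing. Bias in the contrast, 400,000 pairs per setting:

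| SD | OR | Correlation | Random pair effect | Fixed pair effect | Random pair + 4-month change |
|---|---|---|---|---|---|
| 5 | 2 | 0.6 | -0.28 | -0.01 | -0.01 |
| 5 | 2 | 0.8 | -0.21 | -0.01 | 0.00 |
| 5 | 3 | 0.6 | -0.38 | 0.00 | 0.01 |
| 5 | 3 | 0.8 | -0.33 | -0.01 | 0.00 |
| 7 | 2 | 0.6 | -0.40 | -0.02 | -0.02 |
| 7 | 2 | 0.8 | -0.31 | -0.01 | -0.02 |
| 7 | 3 | 0.6 | -0.56 | -0.01 | -0.01 |
| 7 | 3 | 0.8 | -0.45 | -0.01 | -0.01 |

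Maximum likelihood with an unrestricted covariance for the pair's 12- and 18-month values gave 0.16-0.54 in size. The sign reverses if the weight-driven arm is GLB+.

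**Step 3, drop-out driven by unseen 18-month weight, same function in both arms.** logit P(missing) = a - ln(OR) x (loss - 6)/SD, with a set to give 20% overall and true means 7 and 5. By numerical integration, among completers:

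| SD | OR | Missing GLB+ / GLB | Mean loss overstated GLB+ / GLB | Contrast (true 2) |
|---|---|---|---|---|
| 5 | 2 | 17.9% / 22.1% | 0.58 / 0.71 | 1.87 |
| 5 | 3 | 17.0% / 23.0% | 0.80 / 1.05 | 1.75 |
| 7 | 2 | 18.5% / 21.5% | 0.84 / 0.96 | 1.88 |
| 7 | 3 | 17.9% / 22.1% | 1.17 / 1.42 | 1.75 |

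The contrast shrinks by 0.12-0.25 because the arm with less loss drops out more. Where the 12-month weight is observed and used, the overstatement is smaller: 0.18-0.70 points in a simulation with both missing rates fixed at 20% and a 12-18 month correlation of 0.7 or 0.85.

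**Step 4, what 4-month weight cannot repair.** With unseen 18-month weight driving drop-out in GLB only (SD 7, 20% missing, 150 pairs, correlation of 4- and 18-month change 0.65, latent correlation of drop-out with weight 0.5), the random-pair model estimated a true 2.0 as 0.93. Adding 4-month change gave 1.26.

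**Step 5, tipping-point arithmetic.** Let delta be the amount by which missing people differ from the MAR prediction. Shift in contrast = missing fraction x (delta in GLB+ - delta in GLB). At 20% missing, 2 points are erased at a delta difference of 2/0.2 = 10 points; at 10%, 2/0.1 = 20; at 30%, 2/0.3 = 6.7. Significance would be lost earlier, at a point that depends on sample size and SD.

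**The case against.** The strongest reply is that a mixed model under MAR is standard, that section 15.1 separately says MAR is anticipated, and that the rate comparison alters no estimate. This stands, and it limits the fault in the rule to its reasoning and its missing branch.

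Second, the pairing may already protect the contrast. Section 15.3 does not say whether pair effects are fixed or random. With fixed effects, the bias in step 2 is about zero. This also stands for well-matched pairs, so a reader should not infer that leaving 4-month weight out of the model necessarily biases the randomised comparison. It does not cover drop-out driven by unseen weight.

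Third, 4-month change could be picked as a significant covariate, and the cost-effectiveness sensitivity analyses might vary weight inputs. Neither is a commitment, and the latter would not test the Aim 2 result. The retention measures in section 5.0 and the follow-up of missing instruments in section 15.1 reduce missingness but do not show how far the conclusion depends on it.

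Fourth, arm means are secondary, since no test against 7% is planned. This is fair, but section 15.4.2 uses them.

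Finally, a 10-point delta difference is large, so the point estimate need not be fragile. That is so at 20% missing, but the actual rate is unknown.

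**Conclusion.** The concern holds in a limited form. The inference from a non-significant rate comparison to MAR is invalid whatever the numbers. The consequential gaps are the absence of a commitment to 4-month change in the Aim 2 models and of any not-at-random analysis of trial weights.

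Under the assumptions above, 4-month-driven drop-out in one arm biases the contrast by about 0.2-0.6 points when pair is random or handled by likelihood across incomplete pairs, and by about zero when it is fixed. Naming 4-month change removes the bias under the former handling. Unseen-weight drop-out that is alike in both arms overstates completers' mean loss by about 0.6-1.4 points and shrinks the contrast by about 0.1-0.25.

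Two tempting readings go too far. One is that the Aim 2 result will be biased, or biased in a known direction: the documents say nothing about who drops out, or whether the mechanism differs by arm, which a larger contrast bias would need. The other is that an identical mechanism in both arms leaves the contrast exactly unbiased: with hypothesised means of 7% and 5% it does not. This is worth correcting but does not invalidate the trial.

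**What to change.** 1. In section 15.1, delete the significance test as a gate. State MAR as an assumption of the likelihood-based mixed model fitted to all randomised participants. Missing rates by arm can still be reported descriptively.
2. In section 15.3, name 4-month percent weight change in the first Aim 2 model and 4-month weight in the absolute-weight model. Keep the pairing, and say whether pair effects are fixed or random.
3. Prespecify one not-at-random sensitivity analysis of 12- and 18-month weight, such as a delta-adjusted tipping point with delta allowed to differ by arm. Report arm means as well as the contrast.

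The cost is SAP wording and modest programming. No new measurement is needed, since 4-month weight is already collected for the matching. The downside is that the conclusion may look less certain, and a tipping point gives a range rather than one answer.

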#### ***15.2 Specific Aim 1 Analysis***

It is hypothesized that there will be no significant difference in percent weight change at four months between treatment groups due to the enhanced training provided to early non-responders. A test of equivalence of the two treatments with percent weight change as the response variable will be performed. A stepwise regression model with

Bayes Information Criterion for choosing the final model will be built. Final test of equivalence will be carried out at level of significance 0.05.

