## **2.0 Brief Overview of the Study Protocol**

The purpose of this study is to implement and evaluate a lifestyle intervention for Ohio State University (OSU) employees with prediabetes to determine the impact of the intervention on weight loss and related outcomes to reduce risk for type 2 diabetes mellitus (T2DM). People with prediabetes are at high risk for progressing to T2DM, and weight loss is the most effective treatment for risk reduction. This study trial follows a preliminary trial to evaluate the efficacy of a lifestyle intervention implemented at a university worksite. The efficacy trial was highly successful in promoting weight loss on average among participants randomized to the experimental group. However, about 50% of experimental participants did not achieve clinically meaningful weight loss. More effective treatments are needed for people who are slower to respond to behavioral interventions. A goal of this trial is to determine whether augmented care for slow responders promotes greater weight loss and risk reduction. Effective weight loss maintenance interventions also are needed to reduce risk for T2DM. We will examine the impact of an extended intervention phase on weight loss maintenance following an intensive lifestyle intervention.

The specific aims of this translational study at a university worksite are to:

**Specific Aim 1:** Implement the first 4-sessions of the core 16-session phase of the Group Lifestyle Balance (GLB) intervention for diabetes prevention to all study participants. GLB is the group-based version of the intervention implemented in the Diabetes Prevention Program. Determine percent weight change at week 5. Provide a 12-session augmented intervention (called Group Lifestyle Balance Plus (GLB+)) to participants who fail to achieve > 2.5% weight loss at week 5; provide the remainder of the 12-session standard GLB intervention to all other participants. GLB+ will be enhanced with training in values clarification, mindful decision making, planning, and problem solving. Evaluate the impact of the augmented GLB+ intervention to the standard GLB intervention immediately following the core intervention phase (4 months from baseline).

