### **4.0 Study Flow Diagram**

An overview of the general study processes is provided in Figure 1. In this trial, participants are not randomized to treatment group at baseline. Instead, all participants receive the first four weeks of the standard GLB intervention. During these first four weeks, participants learn basic skills such as self-monitoring, the calorie and fat content of food and beverages, and how to initiate a physical activity program such as brisk walking. Participants then remain in the standard GLB intervention if they achieve at least 2.5% weight loss at week 5. If participants do not achieve this level of weight loss, they will be stratified to the augmented GLB+ intervention at week 5. Participants will be randomized to treatment group following the core intervention phase (first 16 weeks) for the extended (8 months) and maintenance (6 months) intervention phases.

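### Aim 1's equivalence test compares early non-responders (all on GLB+) with early responders (all on GLB), so unless week-5 weight change is in the model, neither a pass nor a fail shows whether GLB+ worked

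*Combined protocol and SAP*

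**What the plan says.** Section 2.0 sets the purpose of Aim 1: "Evaluate the impact of the augmented GLB+ intervention to the standard GLB intervention immediately following the core intervention phase (4 months from baseline"). Everyone receives the first four GLB sessions. GLB+ then goes to "participants who fail to achieve > 2.5% weight loss at week 5", and all others continue on GLB. Section 7.0 gives the same rule. Section 4.0 confirms that "participants are not randomized to treatment group at baseline", and section 8.0 places the only randomisation after the 16-week core phase.

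Section 15.2 is the only efficacy analysis stated for Aim 1. It hypothesises no significant difference in percent weight change at four months "between treatment groups due to the enhanced training provided to early non-responders". The analysis is: "A test of equivalence of the two treatments with percent weight change as the response variable will be performed". A stepwise regression with "Bayes Information Criterion for choosing the final model will be built", and the final equivalence test is at level 0.05. The section gives no equivalence margin, no list of candidate covariates and no reference weight for the percent change. It does not mention week-5 change.

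**The concern.** At four months no slow responder has stayed on GLB and no early responder has received GLB+. Treatment and early response are therefore the same split of the sample, and the comparison has no randomised or overlapping control.

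The expected similarity could arise because GLB+ helped slow responders to catch up, or because the two groups would have ended close together anyway. A difference could arise because GLB+ failed, or because it worked but did not close a large gap. Section 15.2 takes the first explanation for similarity and writes it into the hypothesis. What is at stake is Aim 1's conclusion on the impact of GLB+ in the core phase.

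**Working it through.** **1. What the contrast estimates.** Let D be mean four-month percent loss on GLB+ minus that on GLB, τ the GLB+ effect in slow responders, and G the amount by which early responders would exceed slow responders if both stayed on GLB. Without week-5 change in the model,

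E(D) = τ − G.

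The contrast alone cannot separate τ from G. If change is measured from baseline, G also includes the early loss that formed the groups. Section 15.2 does not state the reference weight. Baseline is the likelier reading, because section 7.0 sets its weight goals against initial body weight.

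**2. If week-5 change is in the model.** With the GLB+ term kept and a linear relation, the GLB+ coefficient estimates τ at the cut-off. Equivalence then means τ is near zero: GLB+ added little. That is the opposite of what section 15.2 would conclude from a pass. Neither branch supports the planned inference.

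**3. Illustration of size.** The plan has no figure to reproduce. Inputs, all assumed except where noted:

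- Equal groups. Section 2.0 says that in the preliminary trial "about 50% of experimental participants did not achieve clinically meaningful weight loss", but that is a different criterion from the week-5 cut-off, so the share remains an assumption.
- Total N 150-300, from 15-20 cohorts and groups of 10-15 (section 7.0): 15 × 10 = 150 and 20 × 15 = 300. This takes one group per cohort, which the plan does not say.
- Week-5 change normal with SD 2 points; four-month change measured from baseline.
- Slope b, the share of the week-5 difference still present at month 4: 0.5 (four-month SD 4, correlation 0.25) or 1.5 (SD 5, correlation 0.6).
- Margin ±3 points; two one-sided tests at 5%; week-5 change not in the model.
- The benefit of 2 points is borrowed from section 15.3 (7% against 5%), which concerns the extended phase.

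For a cut at the median, G = b × 2 × 1.596, which gives 1.60 for b = 0.5 and 4.79 for b = 1.5.

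Within-group variance = b² × 4 × (1 − 2/π) + SD² × (1 − r²):

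- b = 0.5: 0.25 × 1.4535 + 16 × 0.9375 = 15.36, SD 3.92.
- b = 1.5: 2.25 × 1.4535 + 25 × 0.64 = 19.27, SD 4.39.

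SE = SD × √(4/N). Here E(D) is negative and the upper bound hardly matters, so the chance of a pass is approximately 1 − Φ(z), with z = (−3 + 1.645 × SE − E(D)) / SE.

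| Case | N | E(D) | SE | z | Passes at ±3 |
|---|---|---|---|---|---|
| No effect, gap 1.60 | 150 | −1.60 | 0.640 | −0.55 | 71% |
| No effect, gap 1.60 | 300 | −1.60 | 0.453 | −1.46 | 93% |
| 2-point benefit, gap 4.79 | 150 | 2 − 4.79 = −2.79 | 0.717 | 1.35 | 9% |
| 2-point benefit, gap 4.79 | 300 | −2.79 | 0.507 | 1.22 | 11% |

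A useless GLB+ can usually pass and a useful one can usually fail, depending on G.

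**4. Separate check with other inputs** (week-5 SD 1-1.5, residual SD 4, N 225). A zero effect passed in 72% of simulated trials (gap 0.8, margin ±2) and 84% (gap 1.6, margin ±3). A true 2-point effect with gap 3.6 passed at ±2 in 18%. With week-5 change as a linear covariate, the estimates centred on the true effect, but the SE rose from about 0.55 to 0.89. In one curved example, a zero effect was estimated as 1.36.

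**The case against.** **The stepwise model may pick up week-5 change.** Section 15.2 does not exclude it. In simulations with equal groups, N 150-300, the GLB+ term kept and week-5 change offered as a candidate, BIC selected it in about 37-62% of trials when half the week-5 difference remained at month 4, and in 97% or more when all of it or 1.5 times it remained. This stands as a limit: the illustrated pass rates apply only if week-5 change is not offered or not selected. It does not rescue the plan, because in the other branch a pass has the reverse meaning.

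**Aim 1 may only ask whether slow responders caught up.** That is a legitimate descriptive question, and the unadjusted difference answers it. But section 2.0 speaks of the impact of GLB+, and section 15.2 names the training as the cause.

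**Change might be measured from week 5.** Then the slopes 0.5 and 1.5 become −0.5 and 0.5, and the gap could shrink or reverse. The illustrated sizes would not apply. The comparison would still not be randomised.

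**Stronger readings to avoid.** A reader might infer that an effective GLB+ will be declared significantly worse. Section 15.2 plans an equivalence test, not that directional test, and under assumed inputs the rate of such a result runs from under 1% to 100%. A reader might also infer that a tight margin makes a pass practically impossible. It does not: at ±1, with a gap of 1.6, a 2-point benefit and N 300, about 30% pass. Nor does the fault reach Aim 2, whose GLB against GLB+ comparison in the extended phase is randomised; equally, Aim 2 does not answer the core-phase question.

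**Conclusion.** Wrong as written, and it must be fixed. The conclusion that section 15.2 draws from equivalence cannot follow from its test. This rests only on the allocation rule and the timing of randomisation, both of which the plan states clearly; it needs no assumed number.

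The size of the error is not established. The plan gives no SD, sample size or margin, and the percentages above depend on the assumed week-5 SD, slope, N and margin, on change from baseline, and on week-5 change being absent from the model. They show that the result can mislead in either direction, not how often it will.

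**What to change.** 1. **Needed.** In section 15.2, delete the clause that attributes the absence of a difference to the enhanced training. Report the four-month group difference with a 95% CI, as a description of whether slow responders caught up. Restate Aim 1 in section 2.0 to match, unless step 2 is adopted. Cost: wording only.

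2. **Optional, if an estimate of the GLB+ effect is wanted.** Replace the stepwise equivalence test with a pre-specified regression-discontinuity model: four-month percent change on a GLB+ indicator, always kept, and week-5 percent change centred at the cut-off. Report a 95% CI, add a functional-form check and allow for clustering by intervention group. Cost: one model and its checks. Week-5 change is already determined under section 7.0, but it must be carried into the analysis dataset. Downsides: the estimate is local to the cut-off, depends on functional form and has only moderate precision. Under assumed inputs, with separate slopes on each side of the cut-off, the SE is about 0.65-1.2 points and power for a 2-point effect about 40-84% before clustering, so a null result would be weak evidence.

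3. **Minor.** Sections 2.0 and 7.0 keep on GLB those who lose more than 2.5%, whereas section 4.0 says: "Participants then remain in the standard GLB intervention if they achieve at least 2.5% weight loss at week 5". These passages must be reconciled so that one rule defines the groups. Only exact ties are affected.

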## **10.0 Safety Reporting**

The Check-In Form will be completed by each participant prior to the participant being weighed before the group session begins and at data collection visits. Study staff will note any boxes checked “yes,” indicating a recent illness, injury, hospitalization, or newly prescribed medication. All positive endorsements will prompt completion of the Adverse Event or Serious Adverse Event form. These events may need to be forwarded to the IRB or Safety Officer depending on the seriousness of the occurrence. The Data Safety Monitoring Plan provides a description of adverse events, serious adverse events, and unanticipated events. Please refer to that document for definitions, documents, and reporting procedures. In general, these events will be reported to the PI, IRB, and possibly the Safety Officer as soon as they are identified (no later than 10 days after occurrence per OSU policy).

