#### ***15.4. Analyses for Comparing Treatment Sequence on Weight Loss Maintenance (sub-aim)***

The analysis for this exploratory sub-aim will compare the 4 treatment sequences embedded in the adaptive design on percent weight change at 18-months. The primary comparison of interest is the GLB/GLB

intervention sequence to the GLB+/GLB+ intervention sequence across the 18-month timeframe. Whether the GLB+ intervention during the extended intervention phase is optimal following the core phase, especially for early non-responders, and whether the GLB+ intervention during the extended intervention phase is necessary to promote weight loss maintenance for those who initially achieved the 2.5% weight loss will be determined. The analysis will be based on an analysis of covariance model, using appropriate covariates (e.g., baseline weight), where we will compare the four groups using an F-test and then perform multiple comparisons using Tukey's HSD test.

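### Aim 1 and the exploratory sub-aim use one weight per person, so the plan's likelihood handling of missing data does not reach them and completer contrasts can be biased

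*Combined protocol and SAP*

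**What the plan says.** All references are to the combined protocol and SAP.

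- **Missing data (Section 15.1).** The proportion missing is compared between the two groups. If the difference is not significant, the data are taken to be missing at random (MAR). No action is given if it is significant. The remedy is maximum likelihood in PROC MIXED, and the assumption is worded for one data structure: "We anticipate MAR structure for the repeated measures data".
- **Aim 1 (Section 15.2).** "It is hypothesized that there will be no significant difference in percent weight change at four months between treatment groups". To examine this, "A test of equivalence of the two treatments with percent weight change as the response variable will be performed". The model is "A stepwise regression model with" BIC selection, and "Final test of equivalence will be carried out at level of significance 0.05". No margin is given.
- **How the Aim 1 groups arise (Section 4.0).** They are not randomised. Of those short of the week-5 target: "If participants do not achieve this level of weight loss, they will be stratified to the augmented GLB+ intervention at week 5".
- **Aim 2 (Section 15.3).** The 12- and 18-month values are treated as repeated measures within matched pairs. No other analysis is described in this way.
- **Sub-aim (the second section numbered 15.4).** Four sequences are compared on the 18-month value: "The analysis will be based on an analysis of covariance model, using appropriate covariates (e.g., baseline weight"), followed by an F-test and Tukey's HSD.
- **Weights taken along the way.** Percent change is determined for everyone at week 5 (Section 7.0). People are weighed at make-up sessions (Section 7.0) and at regular sessions and visits (Section 10.0): "The Check-In Form will be completed by each participant prior to the participant being weighed before the group session begins".

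**The concern.** Likelihood estimation protects against MAR dropout only when the model contains the earlier measurements that predict it. With one response per person there is nothing to borrow from, even if the model is run in PROC MIXED. A person with no 4-month weight leaves Aim 1, and a person with no 18-month weight leaves the sub-aim.

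Aim 1 is the more exposed. GLB+ is made up of week-5 slow responders, so a lower mean loss and a different dropout rate in that group are both plausible. Equivalence is the hoped-for result. Suppose GLB+ truly loses less and its poorest losers are the ones who leave. The remaining GLB+ members then look better than the group as a whole, and equivalence becomes easier to declare in the very case where it would be wrong.

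**Working it through.** **No figure to reproduce.** The documents state no SD, dropout rate, sample size, power or equivalence margin. What follows is illustration under stated assumptions. Gap means GLB loss minus GLB+ loss, in percentage points.

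**Step 1: the mechanism.** Completer gap = true gap + (bias in GLB mean) - (bias in GLB+ mean), where bias is the amount by which completers' mean loss exceeds the group's. By numerical integration, with SD 5 and log-odds of a missing weight rising by 0.5 (or 1.0) per SD less loss:

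| Dropout | Bias, slope 0.5 | Bias, slope 1.0 |
|---|---|---|
| 10% | 0.24 | 0.45 |
| 20% | 0.48 | 0.87 |

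Take a true gap of 2.0 (borrowed from Aim 2's 7% vs 5%), 10% missing in GLB and 20% in GLB+:
- Slope 0.5: 2.0 + 0.24 - 0.48 = 1.76.
- Slope 1.0: 2.0 + 0.45 - 0.87 = 1.58 (1.59 before rounding).

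Over SD 4-6 the range is 1.81-1.51. With equal dropout rates and equal dependence on outcome the two biases cancel and the gap stays at 2.0, although both group means are too favourable.

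**Step 2: dropout driven by earlier weights.** Simulation with SD 4.5, dropout depending on a week-10 session loss correlated 0.9 with the 4-month loss, and logistic slopes 0.15-0.35:

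| True gap | Dropout GLB+ vs GLB | Completer gap |
|---|---|---|
| 3.0 | 25% vs 15% | about 2.6-2.8 |
| 3.0 | 30% vs 10% | about 2.2-2.5 |
| 0 | 25% vs 15% | -0.2 to -0.4 |
| -2.0 (GLB+ better) | 25% vs 15% | -2.2 to -2.4 |

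An estimate that also uses the week-10 weight returns about 3.0 in the first two rows. In a separate simulation with dropout driven by week-5 loss, the true gap was 2.44, completers gave 2.14, and using week-5 weights restored 2.44.

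**Step 3: effect on the equivalence test.** Section 15.0 gives no N. If each of the 15-20 cohorts is one group of 10-15 people (Section 7.0), N is 15 x 10 = 150 to 20 x 15 = 300. Assume equal groups, SD 5 and two one-sided tests at 0.05, with the true gap exactly at the margin. The false-equivalence rate is about Φ(bias/SE - 1.645). For N = 300 with 10% and 20% missing, completers number 135 and 120:
- SE = 5 x √(1/135 + 1/120) = 0.627.
- Bias 2.0 - 1.76 = 0.24: Φ(0.24/0.627 - 1.645) = 0.10.
- Bias 2.0 - 1.59 = 0.41: Φ(0.41/0.627 - 1.645) = 0.16.

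Across N 150-300 the rate is 0.08-0.16 instead of 0.05. If missingness relates to outcome only in GLB+, it is 0.13-0.40.

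**Step 4: would Section 15.1's check catch it?** Its power to detect 10% vs 20% missing is about 0.40 at N = 150 and 0.68 at N = 300. Similar proportions would not establish MAR in any case.

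**Step 5: the sub-aim.** Assume a GLB+ minus GLB difference of 2.0, SD 6, and dropout driven by 12-month loss (correlation 0.85, slopes 0.1-0.2). With 15% missing in GLB+ and 25% in GLB, completers give 1.5-1.7. With the rates reversed they give 2.3-2.5. With equal rates they give 2.0. This is a generic difference. The sub-aim's main contrast is GLB/GLB against GLB+/GLB+, whose members also differ in week-5 response.

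**The case against.** Several objections have force.

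- **Exclusion is not stated.** The plan nowhere says that people without the weight are dropped. This follows from the models named, and nothing in Section 15 (imputation, analysis set or sensitivity analysis) prevents it.
- **The Aim 1 direction is conditional.** A reader might infer that dropout always favours equivalence. The documents do not support that. It needs heavier outcome-related dropout in GLB+ and a true GLB+ deficit. The plan's own hypothesis is no difference, and at a zero gap the same dropout pushes the estimate away from equivalence.
- **The sub-aim direction is open.** A reader might infer that its contrast is attenuated. Step 5 shows that it can equally be exaggerated, and nothing in the documents says which arm will lose more people. The sub-aim is also exploratory, and Aim 2 already treats the randomised comparison as repeated measures.
- **The size is modest.** At 25% vs 15% dropout and SD 4.5, the SE of the gap is 4.5 x √(1/63.75 + 1/56.25) = 0.82 at N = 150 and 4.5 x √(1/127.5 + 1/112.5) = 0.58 at N = 300. A bias of 0.2-0.4 is below one SE. Without a margin, its effect on the actual verdict cannot be computed.
- **Recovery of 3.0 is partly built in.** Dropout was generated from the weight that the estimator then used. If dropout depends on the unseen 4-month value, the same estimator gives 2.87-2.94 at 25% vs 15%. That is closer than completers, but not unbiased.
- **A completer regression can be valid** if it keeps every driver of missingness. BIC selection does not guarantee this. Week-5 loss is also what defines the Aim 1 groups, so adjusting for it changes the comparison.
- **Session weights have limits.** Section 12.2 schedules evaluation at baseline, 4, 12 and 18 months, so session weights may not be in the research dataset. People who stop attending also stop being weighed.

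These points limit the direction and the size. They do not bring the two analyses under Section 15.1's remedy.

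**Conclusion.** The gap is real. As worded, Aim 1 and the sub-aim are single-visit models, and the only missing-data method in the plan covers Aim 2 alone. If dropout follows earlier weight loss and differs between groups, completer contrasts are biased.

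In Aim 1 the shift is towards equivalence only if GLB+ truly loses less and its poorest losers leave more often. It is then about 0.2-0.4 points on a gap of 3.0 at 25% vs 15% dropout. With a zero gap, or one favouring GLB+, it goes the other way. With equal dropout and equal dependence on outcome there is none. In the sub-aim neither direction nor size can be settled from the documents.

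The structural conclusion rests on the text. Every size rests on assumed values. The change is worth making because it is cheap and uses a method the plan already names. It matters more for Aim 1 than for the sub-aim.

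**What to change.** **Aim 1.** Include everyone classified at week 5. Fit a PROC MIXED model of percent weight change at week 5, at a few core-phase sessions named in advance, and at the 4-month visit, with group-by-time means. Use an unstructured covariance, with a named structured fallback if it does not converge, and allow session weights their own residual variance. Selecting only a few sessions keeps the covariance estimable: about 13 occasions, unstructured, would need 13 x 14 / 2 = 91 parameters. Run the equivalence test on the model's 4-month GLB versus GLB+ contrast. The margin for that test also has to be stated, which is a separate need.

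**Sub-aim.** Replace the 18-month ANCOVA with a four-group PROC MIXED model of the 4-, 12- and 18-month percent changes. Read the 18-month contrasts from it and keep the Tukey adjustment. Matching requires the 4-month weight, so everyone randomised as described will have at least one value.

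**Both.** Add a simple sensitivity analysis for missingness that depends on the unseen weight, for example by making the missing values progressively worse in one group and reporting when the conclusion changes. In Section 15.1, do not let the comparison of missing proportions decide whether MAR holds.

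**Cost.** SAP wording, entry of session weights already taken (assuming they were recorded), and some added noise, because session weights are less controlled than visit weights. No new visits or measurements are needed.
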